2. REPORT OF PRIOR INVESTIGATIONS

For prior investigations with Medtronic DMF 2010 – Activa PC+S Neurostimulation System, please refer to Medtronic Right of Reference Letter located in **Appendix B** and [REDACTED] Master File # [REDACTED] (PDF Page 58).

Clinical investigations of the standard DBS system

The [name] Lab has performed several clinical investigations using the FDA approved Medtronic device, the Activa PC Deep Brain Stimulation (DBS) system, since 2005. From here on, this term - the DBS system - will refer to the standard (nonsensing) implantable pulse generator (IPG), its connectors, leads and the four electrodes that are implanted in the brain. We were the first to show that the presumed brain biomarker of Parkinson's disease (PD), specifically the beta rhythm, was attenuated after short periods of DBS¹. We subsequently showed that the resting beta rhythm was stationary and was similar across hemispheres in individuals but different among people with PD, and that there was evidence that this abnormal rhythm in the brain in PD was a property of a widespread bilateral sensorimotor network^{2,3}. We demonstrated that there was a gradient in the power of this rhythm within the main target nucleus for DBS in PD, the subthalamic nucleus (STN), and that DBS both at this site and dorsal to the nucleus attenuated the beta rhythm power in a voltage-dependent fashion in PD and showed prolonged attenuation of beta power after longer periods of DBS^{2,4,5}. We have also reported that such abnormal electrophysiology is seen in both primary and secondary dystonia in the brain and that DBS also attenuates beta rhythm power in dystonia in the target nucleus, the globus pallidus interna (GPI). We are in the pilot stages of our investigations of abnormal electrophysiology during tremor and movement and the effects of DBS on such. With the technological development of the sensing IPG, we will be able to move these experiments from the operating room to the laboratory.

3. INVESTIGATIONAL PLAN (Study 2: Adaptive Closed Loop

Neuromodulation for Parkinson's Disease)

3.1. Purpose

Deep brain stimulation (DBS) of the subthalamic nucleus (STN), internal segment of the globus pallidus (GPi), and/or thalamus has become the standard of care FDA-approved treatment for Parkinson's disease (PD), tremor, and dystonia. DBS consists of the implantation of chronic stimulating electrodes (leads) - Medtronic models 3387 or 3389 - into the nucleus of choice. The DBS leads are connected to an implantable neurostimulator called Activa PC (already FDA approved). Medtronic has developed a new DBS implantable system called Activa PC+S. Activa PC+S will have therapy equivalent to Activa PC.

Activa PC+S's new sensing capability allows for chronic recording of neural activity in the presence of stimulation or when stimulation is turned off. Furthermore, the new device permits non-invasive data transfer of recorded neural signals.

The Nexus-D system is a newly developed research technology allowing for bidirectional communication of information between the Activa® PC+S and a portable computer (PC).

Currently, cDBS is limited to "open-loop" stimulation without real-time adjustment for the patient's state of activity, fluctuations and types of motor symptoms, medication dosages, or neural markers of the disease. The purpose of this proposed study is to determine if an adaptive DBS system, responding to patient-specific clinically relevant neural or kinematic feedback, is more effective than continuous DBS on the motor Unified Parkinson's Disease Rating Scale (UPDRS III) and specific phenotypic measures in Parkinson's Disease.

Used in conjunction, the Nexus-D and Activa® PC+S devices will allow us to begin to investigate "closing the loop" and will allow for the implementation of adaptive neuromodulation (aDBS) which adjusts stimulation parameters in real-time to account for patients' symptoms and actions. The Nexus-E system firmware update, when used in conjunction with Nexus-D, allows for neural recording without data compression in order to analyze the effect of adaptive DBS on LFP power.

Currently, there are a myriad of possible algorithms to inform aDBS based on numerous potential kinematic and neural options for use as input signals. Preliminary studies have shown improvement in items of the motor Unified Parkinson's Disease Rating Scale (UPDRS III), and predicted decreased energy when using aDBS triggered by resting state beta band (13-30 Hz) peak power compared to continual feed-forward DBS and randomized stimulation¹. However, it is unknown if peak beta power is the optimal neural classifier for tremor, bradykinesia, freezing, and/or when the patient is undergoing their activities of daily life. The tools available in the Activa® PC+S, Nexus-D and Nexus-E System will allow the opportunity to test such algorithms within safe and externally-controlled boundary conditions for the first time in human subjects with PD.

3.2. Protocol

3.2.1 Background and significance

The proposed study will mark the first clinical implementation of the Nexus-D/E device to create a closed-loop stimulation system. Neuromodulation and changes of stimulation parameters will be implemented by computer algorithms using neural and kinematic triggers

imputed to the PC and communicated to the Activa® PC+S neurostimulator using the Nexus-D/E system.

Concurrent synchronized kinematic signals will be recorded using an analog-to-digital converter (CED, Cambridge Electronic Design Limited, Cambridge, England). These will be used to determine classifier algorithms for the states of tremor or bradykinesia using angular velocity sensors strapped to the hands. Patient-specific kinematic triggers of tremor amplitude and movement velocity will be used to trigger aDBS. By optimizing neurostimulation outside the clinical setting, aDBS will reduce the number of office visits and travel for many PD patients. The ideal aDBS system would also adjust to therapies and motor states over time, preventing harmful side effects. Additionally, aDBS may allow for significantly less total energy delivered compared to cDBS since neurostimulation is only turned ON when disease-pertinent classifiers are present. This should prolong battery life and reduce the necessity and frequency of neurostimulator replacement surgeries which reduces overall surgical risk. Adaptive or “intelligent” deep brain stimulation will allow for the continuous optimization of therapy on an individual basis, maximizing motor improvement and minimizing adverse effects.

We believe that the field of neurostimulation is about to undergo a significant paradigm shift, similar to the revolution in cardiac pacing when demand-based pacemakers were realized that could pace the heart in response to abnormal heart rhythms. This research will allow us to identify the abnormal brain signals or brain “arrhythmias” responsible for abnormal motor behavior in PD and will ultimately allow the design of demand or feedback brain pacemakers.

3.2.2 Specific Aims

SA1: Determine the efficiency and effectiveness on PD signs of aDBS, triggered by patient-specific resting or movement state neural activity, compared to cDBS, using the UPDRS III and validated high-resolution kinematic metrics of tremor, bradykinesia and freezing of gait (FOG).

Primary Hypothesis: Resting state aDBS will reduce energy consumption compared to cDBS as well as improve overall motor outcome, but may have differing effects on the individual PD motor signs.

SA1a. Determine the neural classifier of the resting or movement state to use as a trigger for aDBS. Hypothesis: Patient-specific beta band synchrony is a classifier of the off therapy resting or movement state in PD and can be used as a trigger for aDBS^{1,2}. Using individualized algorithms, resting or movement state neural activity will be tested as the stimulation trigger, activating aDBS when beta power is above a specific threshold. SA1b. Compare the efficiency and effectiveness on PD symptoms of aDBS (using the patient specific resting state neural classifier) compared to cDBS at the same neurostimulation parameters.

SA2: Determine whether aDBS using a kinematic classifier pertinent to the patientspecific phenotype is more efficient and/or effective on PD symptoms than aDBS using the using the patient’s specific resting or movement state neural classifier and/or cDBS.

Secondary Hypothesis: Different PD motor phenotypes may respond better to aDBS triggered by the kinematic classifier respective to that state than to aDBS triggered by the resting or movement state neural classifier or to cDBS.

SA2a. Determine the kinematic classifiers for the states of tremor and bradykinesia, and develop the control policy algorithms of optimal DBS settings that improve each motor abnormality. SA2b. Compare the efficiency and effectiveness on PD symptoms of tremor or bradykinesia kinematic aDBS versus resting or movement state neural aDBS and cDBS.

SA3: Determine whether aDBS is more efficient and effective than cDBS in the optimized on medication state after six months of cDBS.

Tertiary Hypothesis: Neural and/or kinematic classifiers and control policy algorithms will need to be adapted to different medication states, making aDBS more or less useful. After six months of cDBS plus medication, SA1 and SA2 will be repeated in the optimized on medication state. The control policy algorithms will be adjusted as necessary to adapt to this state.

3.2.3 Study Design, Setting/Location

This is an open-label pilot study of up to 30 people with Parkinson's disease. All experiments will be performed in the Stanford Human Motor Control and Balance Laboratory in the department of Neurology and Neurological Sciences at Stanford University Medical Center. A unique aspect of the Stanford Movement Disorders Center is the Stanford Human Motor Control and Balance Laboratory, in which we have developed several quantitative measures of motor control and a parallel line of research in human motor control in movement disorders. These measures have been validated with the clinical scale most widely used in PD research, the UPDRS III, as stated above.

Study Population

The study will be carried out in up to 30 people with moderate to advanced PD who will have been evaluated and approved to have subthalamic deep brain stimulation to treat their motor signs. Subjects who have been implanted with Activa PC+S and are participating or have completed Study 1 will be asked to complete Study 2. In order to account for study attrition additional subjects (up to 30) will be recruited into study 2.

Battery life on the Activa PC + S (research device) and the Activa PC (FDA-approved clinical device) is estimated to last approximately 3-5 years. A limited number of subjects will be invited to be replaced with an Activa PC+S, should they chose to remain in the study. Invitations to receive a replacement Activa PC+S will depend on the focus of future experiments, quality of signal, and device availability. If the patient would prefer not to continue in the study, or if they are not invited to continue, they may proceed with the standard implantation of the non-research device.

3.2.4 Eligibility Criteria

The eligibility criteria are the same as those used for Study 1

Inclusion criteria:

1. A diagnosis of idiopathic Parkinson's disease with bilateral symptoms at Hoehn and Yahr Stage \geq II.
2. Documented improvement in motor signs on versus off dopaminergic medication, with a change in the Unified Parkinson's Disease Rating Scale motor (UPDRS III) score of \geq 30% off to on medication.
3. The presence of complications of medication such as wearing off signs, fluctuating responses and/or dyskinesias, and/or medication refractory tremor, and/or impairment in the quality of life on or off medication due to these factors.
4. Subjects should be on stable doses of medications, which should remain unchanged until the DBS system is activated. After the DBS system is optimized (during which time the overall medication dose may be reduced to avoid discomfort and complications such as dyskinesias), the medication dose should remain unchanged, if possible, for the duration of the study.
5. Treatment with carbidopa/levodopa and with a dopamine agonist at the maximal tolerated doses as determined by a movement disorders neurologist.
6. Ability and willingness to return for study visits at the initial programming and after three, six, and twelve months of DBS.
7. Age > 18

Exclusion criteria:

1. Subjects with significant cognitive impairment and/or dementia as determined by a standardized neuropsychological battery.
2. Subjects with clinically active depression, defined according to the Diagnostic and Statistical manual of Mental Disorders, Fourth Edition (DSM-IV) criteria and as scored on a validated depression assessment scale.
3. Subjects with very advanced Parkinson's disease (Hoehn and Yahr stage 5 on medication (non-ambulatory)).
4. Age > 80 .
5. Subjects with an implanted electronic device such as a neurostimulator, cardiac pacemaker/defibrillator, or medication pump.
6. Subjects who are pregnant, are capable of becoming pregnant, or who are breast feeding.
7. Subjects with an MRI showing focal brain lesions that could indicate a non-idiopathic movement disorder.
8. Subjects having a major comorbidity increasing the risk of surgery (prior stroke, severe hypertension, severe diabetes, or need for chronic anticoagulation other than aspirin).
9. Subjects having any prior intracranial surgery.
10. Subjects with a history of seizures.
11. Subjects who are immunocompromised.
12. Subjects with an active infection.
13. Subjects who require diathermy, electroconvulsive therapy (ECT), or transcranial magnetic stimulation (TMS) to treat a chronic condition.
14. Subjects who have an inability to comply with study follow-up visits.
15. Subjects who are unable to understand or sign the informed consent

Subgroups: We will attempt to recruit an equal number of tremor-dominant and tremor absent people as well as an equal number of people with documented freezing episodes and those without. Some with tremor may or may not freeze and vice versa. We will also attempt to recruit women and minorities, although the incidence of PD is higher in men and highest in Caucasians, so with only 30 subjects in this pilot trial, there may be more men than women and more Caucasians than other ethnic groups in our cohort.

3.2.5 Study outcomes

Beta power, UPDRS III, and quantitative measures of tremor (rest tremor recording for 1 minute), bradykinesia (WFE task), speech and FOG (using a Stepping in Place (SIP) task⁴/Gait Analysis), and time DBS ON over the time on aDBS.

3.2.6 Recruitment

Subjects with Parkinson's disease who have been accepted for DBS implantation will be asked if they wish to participate in this study. All subjects will have undergone challenged on medication and practically defined off medication evaluations by a fellowship-trained movement disorders neurologist and detailed neuropsychological testing by a neuropsychologist prior to being presented at the movement disorders surgical review board. The movement disorders surgical review board consists of the neurosurgeons, movement disorders neurologists, psychiatrist, neuropsychologist, and nurse specialists, who evaluate each candidate's suitability for surgery and reach a consensus decision about each person. If s/he is accepted for DBS, s/he is scheduled to meet the neurosurgeon. At this visit they will be met in person by the research coordinator, who will with permission sit down in person with them and any family present to explain the study and review the informed consent. Feasibility of and time for recruitment: on average the Stanford Movement Disorders Surgical Review board accepts 6 – 10 patients for DBS per month. If it is assumed conservatively that 50% of patients asked will consent, then the recruitment of 15 subjects will take a maximum of five months. We recruit subjects currently for intra-operative investigations, which we think would be harder to recruit for than the current study and our acceptance rate is higher than 80%.

We will also recruit subjects who are participating in or have completed Study 1 to consent to and complete Study 2. In order to account for study attrition additional subjects (up to 10 additional) will be recruited into study 2.

Sample Size/Power Analysis: Our preliminary data: change ON versus OFF DBS (mean +/- std dev): beta band power = 57 +/- 6², UPDRS = 58 +/- 22%⁵, Vrms 45% +/- 63%³. Power analysis (paired t-test, p=0.8, alpha =0.001, to allow for multiple comparisons) on the above data gave the largest sample size required for significant outcomes = 27 (STNs), which is similar to the sample size (21) needed to detect difference between aDBS and cDBS reported in previously published results¹.

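### The stated 27 STNs does not follow from the printed alpha, power and Vrms change, which require 39 STNs (two-sided) or 36 (one-sided)

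*Combined protocol and SAP*

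**What the plan says.** The sample-size paragraph in 3.2.6 (Recruitment) lists preliminary changes between DBS ON and OFF, labelled as mean and standard deviation: beta band power 57 ± 6, UPDRS 58 ± 22%, Vrms 45% ± 63%. It then states: "Power analysis (paired t-test, p=0.8, alpha =0.001, to allow for multiple comparisons) on the above data gave the largest sample size required". The figure it reports is 27, counted in STNs. The sentence goes on to compare that number with a published one, "which is similar to the sample size (21) needed to detect difference between aDBS and cDBS reported in previously published results". It does not say whether the test is one- or two-sided.

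Two other statements bear on how the number is used. The feasibility text in 3.2.6 reckons that "then the recruitment of 15 subjects will take a maximum of five months". Section 3.2.3 sets the ceiling: "This is an open-label pilot study of up to 30 people".

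**The concern.** The paragraph prints everything needed to repeat the calculation except sidedness, and repeating it does not return 27 under either choice. Alpha 0.001, 80% power, the Vrms change and 27 STNs cannot all be true together.

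This is the only sample-size calculation worked in the protocol. The strict alpha is there for a stated reason, "alpha =0.001, to allow for multiple comparisons". If 27 was in fact obtained at a looser alpha, it does not carry the multiplicity protection claimed for it. The same sentence also uses 27 to claim agreement with the cited 21, the protocol's only benchmark for aDBS against cDBS, which is the contrast the aims address.

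**Working it through.** **Inputs (all from 3.2.6).** Paired t-test; alpha 0.001; power 0.8 (printed as p=0.8, and power is the only sensible reading); mean and SD of the within-unit change for three outcomes. Sidedness is not given, so both cases are shown. STNs are treated as independent, as the stated unit implies.

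**Formula.** For a paired t-test, d = mean change / SD of change. With n units, the test statistic is noncentral t with n − 1 degrees of freedom and noncentrality d√n. The required n is the smallest that gives power of at least 0.80.

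**Which outcome drives the largest n** (alpha 0.001):

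| Outcome | d | n two-sided | n one-sided |
|---|---|---|---|
| Beta power | 57/6 = 9.5 | 4 | 4 |
| UPDRS | 58/22 = 2.64 | 8 | 7 |
| Vrms | 45/63 = 0.714 | 39 | 36 |

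Vrms sets the maximum. The steps around its threshold are:
- Two-sided: n = 38 gives power 0.785 and n = 39 gives 0.803.
- One-sided: n = 35 gives 0.799 and n = 36 gives 0.816.

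**Attempt to reach 27 at the printed alpha and power.**
- Normal approximation, n = ((z for alpha + z for power)/d)². Two-sided: ((3.291 + 0.842)/0.714)² = 33.5, so 34. One-sided: ((3.090 + 0.842)/0.714)² = 30.3, so 31.
- Rounding of the inputs (mean 44.5 to 45.5, SD 62.5 to 63.5): 38 to 41 two-sided, 34 to 37 one-sided.
- Two-sample formula: 67 per arm two-sided, 61 one-sided.
- 63% read as a per-condition SD: about 27 is reached only with an assumed within-pair correlation of roughly 0.65 to 0.7. The text labels the values as the change and gives no correlation.

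**Power that 27 STNs provide at alpha 0.001.** The noncentrality is 0.714 × √27 = 3.71. The two-sided critical value on 26 degrees of freedom is also 3.71, so power is close to one half: 0.515 two-sided. One-sided it is 0.611. A simulation agreed (0.517 and 0.613).

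**What does give 27.**
- Alpha 0.01 two-sided, equivalent to 0.005 one-sided, with the printed Vrms input: n = 26 gives 0.794 and n = 27 gives 0.815.
- Alpha 0.005 two-sided under the normal approximation also gives 27, although the exact test then needs 31.
- Alpha 0.001 with a larger effect: d = 0.888 two-sided (for example, mean 45 with SD 50.7) or d = 0.834 one-sided (mean 45 with SD 54.0).

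**Consequences for the other figures.**
- Ratio to the cited 21: 27/21 = 1.29; 36/21 = 1.71; 39/21 = 1.86.
- If implants are bilateral (assumption), 15 subjects give 30 STNs, with power 0.60 two-sided or 0.69 one-sided.
- On the same assumption, 30 subjects give 60 STNs, with power 0.98 two-sided or 0.99 one-sided.

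**The case against.** The arithmetic is not in dispute; the objections concern what follows from it.

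- **Nothing shows which element is wrong.** If the printed alpha is the slip, 27 is right and the comparison with 21 is unaffected. A one-digit slip in the SD would also do it: 45 ± 53% gives 27 one-sided at alpha 0.001 (power 0.819). The calculation may also have been run on the underlying paired values. This stands. The figures 39 and 36 are the requirement only if the printed alpha and Vrms input are both correct. It does not rescue the paragraph, which says that the printed data produced 27.
- **The comparison with 21 is loose.** The unit of the 21 is not stated, so the ratios may set STNs against people. This stands; the ratios are illustrative.
- **Fifteen subjects is a recruitment-rate illustration.** The plan also draws on Study 1 participants and allows up to 30 people. This stands too, so the power at 30 STNs describes a scenario and not the planned sample.
- **The reassurance at 60 STNs assumes independence.** Section 2 reports that the resting beta rhythm is similar in the two hemispheres of a person. That concerns beta, not Vrms, but it makes independence doubtful. Under an assumed within-person correlation of 0.5, 60 STNs carry the information of 60/1.5 = 40, with power about 82% two-sided. At 0.8 they carry 60/1.8 = 33, with power about 68%. This qualifies the reassurance. It does not bring 27 any closer to the printed inputs.
- **It is a pilot, and the calculation concerns ON versus OFF, not aDBS versus cDBS.** This limits the consequences. A plan that states a formal alpha, power and sample size still needs the three to agree.

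**Conclusion.** The concern holds as a mismatch between a stated sample size and its own stated inputs. At alpha 0.001 and 80% power, the printed Vrms change requires 39 STNs two-sided or 36 one-sided, which is 12 or 9 more than the 27 stated. Put the other way, 27 STNs give about 52% or 61% power, not 80%. The conclusion rests on reading p=0.8 as power, on the values being the mean and SD of the change as labelled, and on independent STNs. It does not depend on sidedness or on rounding.

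The cause cannot be identified from the documents. The point should be fixed, but it does not invalidate the design, and the correction alone gives no reason to raise the ceiling of 30 people.

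**What to change.** In the sample-size paragraph of 3.2.6, state sidedness and that 0.8 is the power, then take whichever course matches what was done:

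- If alpha 0.001 and Vrms 45 ± 63% stand, restate the requirement as 39 STNs (two-sided) or 36 (one-sided), or keep 27 and state its power as about 52% or 61%.
- If the calculation used alpha 0.01 two-sided (0.005 one-sided), correct the printed alpha and say whether that level still covers the multiple comparisons intended.
- If another Vrms mean or SD was used, print it.

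Then reconsider the claim of similarity to the cited 21, and say whether that number counts STNs or people. The cost is one or two sentences, with no change to procedures or to the enrolment ceiling.

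### The required 27 STNs does not follow from its stated inputs (39 two-sided, 36 one-sided), and the calculation concerns DBS ON versus OFF, not aDBS versus cDBS

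*Combined protocol and SAP*

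**What the plan says.** Section 3.2.6 (Sample Size/Power Analysis) opens with "Our preliminary data: change ON versus OFF DBS (mean +/- std dev") and lists three outcomes: beta band power 57 ± 6, UPDRS 58 ± 22%, and Vrms 45% ± 63%. A paired t-test with p=0.8 (read here as power) and "alpha =0.001, to allow for multiple comparisons) on the above data gave the largest sample size required for significant outcomes = 27 (STNs") follows. The sentence ends with a comparison: "which is similar to the sample size (21) needed to detect difference between aDBS and cDBS reported in previously published results". Nothing more is given about the 21. Sidedness is not stated, and STNs are not converted to patients.

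On study size, section 3.2.3 says "This is an open-label pilot study of up to 30 people", and section 3.2.4 repeats the number: "with only 30 subjects in this pilot trial". Section 3.2.6 estimates recruitment time for a smaller group: "the recruitment of 15 subjects will take a maximum of five months". The allowance for attrition appears as "additional subjects (up to 30) will be recruited into study 2" in section 3.2.3 and as "additional subjects (up to 10 additional) will be recruited into study 2" in section 3.2.6.

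Section 3.2.2 sets the efficacy comparisons. SA1b compares neural aDBS with cDBS at the same stimulation parameters. SA2b compares kinematic aDBS with neural aDBS and with cDBS. SA3 compares aDBS with cDBS on medication after six months of cDBS.

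**The concern.** There are three separate problems.

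- **The arithmetic.** Apart from sidedness, the paragraph gives everything needed to repeat the calculation, and a mean change of 0.71 SD at alpha 0.001 looks too small to be detected with 27 units.
- **The contrast.** Turning stimulation on after it has been off has a large effect. Two active stimulation modes, in SA1b at the same parameters, cannot be assumed to differ by as much. Power for the first contrast says nothing about the second.
- **The unit.** Two STNs in one patient are not two independent observations, and UPDRS III is a score for the whole patient. A count of STNs cannot be read as a count of patients.

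A reader would take this paragraph to mean that the study has 80% power at an alpha already adjusted for multiplicity. A null result for aDBS against cDBS could then be read as evidence of no difference, when no checkable power statement covers that comparison.

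**Working it through.** **Inputs, all from section 3.2.6.** Paired t-test; power 0.80; alpha 0.001; mean and SD of change for three outcomes. The standardised change is d = mean / SD:

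- Beta power: 57/6 = 9.50
- UPDRS: 58/22 = 2.64
- Vrms: 45/63 = 0.714

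**Attempt to reproduce 27.** Power comes from the noncentral t distribution with n − 1 degrees of freedom and noncentrality d√n. At alpha 0.001, beta power needs 4 and UPDRS 8 (two-sided), so Vrms sets the largest n:

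| Vrms, target 80% power | Power at n | n needed |
|---|---|---|
| alpha 0.001, two-sided | 0.785 at 38; 0.803 at 39 | 39 |
| alpha 0.001, one-sided | 0.799 at 35; 0.816 at 36 | 36 |
| alpha 0.01, two-sided | 0.794 at 26; 0.815 at 27 | 27 |

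The normal approximation, n = ((z_alpha + z_power)/d)², is too optimistic at this size but still does not reach 27:

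- Two-sided: ((3.291 + 0.842)/0.714)² = 33.5, so 34
- One-sided: ((3.090 + 0.842)/0.714)² = 30.3, so 31

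Rounding of the inputs does not explain the gap. With 45.5/62.5 the requirement is 38 two-sided (34 one-sided); with 44.5/63.5 it is 41 (37).

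**Power at 27, alpha 0.001.** 0.515 two-sided and 0.611 one-sided. The chance of missing the planned Vrms change is therefore 48% or 39%, against the 20% implied. The two-sided alpha at which 27 gives exactly 80% is 0.0087.

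**From STNs to patients.** Assume two usable STNs per patient, a t-test on patient means, and a between-side correlation rho, which the documents do not give. Averaging two sides changes d to d / √((1 + rho)/2). At alpha 0.001:

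| rho | d of patient mean | Patients needed, two-sided (one-sided) | Two-sided power, 30 patients | Two-sided power, 15 patients |
|---|---|---|---|---|
| 0 | 1.010 | 23 (20) | 96% | 45% |
| 0.5 | 0.825 | 31 (28) | 79% | 25% |
| 1 | 0.714 | 39 (36) | 60% | 15% |

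With 30 patients, 80% power holds up to rho = 0.47 two-sided or 0.67 one-sided. The 15-patient column is shown because 15 patients supply 30 STNs, which exceeds 27 but falls short of 39 and 36.

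**The cited 21.** Assuming a two-sided paired test at 80% power, n = 21 corresponds to d = 0.64 at alpha 0.05, 0.81 at 0.01, or 1.04 at 0.001. The figure alone does not show which, if any, applies.

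**What the study could detect for aDBS minus cDBS.** The documents give no effect or SD for this difference, so no sample size can be computed. In units of the SD of the per-patient difference, two-sided:

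| Patients | Detectable at 80% power, alpha 0.001 | Same, alpha 0.05 | 95% CI half-width, t(0.975, n − 1)/√n |
|---|---|---|---|
| 30 | 0.83 | 0.53 | 0.37 |
| 15 | 1.32 | 0.78 | 0.55 |

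**The case against.** The strongest reply is that the error has little practical effect. The 52% power applies at exactly 27 STNs, and the protocol allows up to 30 people, hence up to 60 STNs. On patient means that gives 96% two-sided power for Vrms if the sides are uncorrelated and 79% at a correlation of 0.5. This stands for the ON-versus-OFF contrast, with two limits: 30 is a ceiling with no minimum stated, and the correlation is unknown.

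A second reply is that the protocol does address aDBS versus cDBS through the cited 21. It does, and the lack of detail does not show that those aims are underpowered. It shows only that the claim cannot be checked. Being close to 27 adds no support, since 27 is itself wrong and belongs to another contrast.

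Third, this is a pilot and need not be powered at all. That is true, and a precision statement would be enough. But the protocol chose to make a formal power claim, and that claim should be correct.

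Fourth, ON versus OFF does have a place in the study: section 3.2.7 checks for beta attenuation of at least 40% and uses the OFF-minus-ON differential to set thresholds. This justifies keeping the calculation, correctly labelled, but does not extend it to the efficacy aims.

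Finally, the two attrition figures may not conflict, since the 30 in section 3.2.3 could be the overall ceiling. That is a minor point of clarity and does not affect the calculation.

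**Conclusion.** The concern holds. For the stated test, alpha and power, the requirement is 39 STNs two-sided or 36 one-sided, and no variant tried at alpha 0.001 gives 27. This rests only on the figures in section 3.2.6 and on treating STNs as independent, as the protocol's own calculation does. That alpha 0.01 was actually used is an inference from the matching result; the documents say 0.001.

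The mismatch of contrast is the more serious defect, because a larger sample does not cure it: SA1b, SA2b and SA3 have no power statement that can be verified. The conversions to patients depend on the assumed two STNs per patient and between-side correlation. This should be fixed, but it does not invalidate the design.

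**What to change.** Revise the sample-size paragraph in section 3.2.6:

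1. Replace 27 with 39 (36 if one-sided). Alternatively, keep 27 and correct what is stated beside it: two-sided alpha 0.01, if that was the level used, or power of 52% two-sided (61% one-sided) at alpha 0.001. The first alternative needs a reason why 0.01 is strict enough for the multiple comparisons; the second concedes that 27 is too few for 80%. State the sidedness in any case.
2. Say that the calculation is for DBS ON versus OFF and does not power the comparisons in SA1b, SA2b and SA3.
3. Give the outcome, effect, SD, alpha, power and unit behind the 21, or remove it.
4. State the planned number of patients and, for the per-patient aDBS-minus-cDBS difference, either the detectable standardised difference at 80% power or the 95% CI half-width in SD units. The last table in the working supplies these for 30 and 15 patients.
5. Count patients rather than STNs for UPDRS III, and state the between-side correlation assumed when converting STNs to patients. Use one attrition figure in sections 3.2.3 and 3.2.6.

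The cost is protocol wording and a less favourable power statement. No extra patients are needed.
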